4.	9.9	
NCI and the CTSU would be happy to have a call with the E-A to brainstorm strategies to increase awareness of the importance of outreach to Black or African American patients and physicians to consider participation in this trial given their higher incidence rates of multiple myeloma . Contact [name] at: [contact]'
 
Response: This is no longer applicable to the study

5.	9 Accrual	
The investigators state that the plan is to increase accrual of Black or African American patients and operationally close the trial to non-AA patients when they reach 150 non-AA patients.
 
A revised plan that changes the study number to 150 should be included in the statistical section, study design, and consent An explanation of why this is being done should be included in the background section.
 
Section 9.8.3 indicates accrual will continue to 180 patients. Which would seem to include 150 patients and 30 AA patients. These numbers however do not include the AA patients included in the first 150. Is the intent to include 30 additional randomized patients, to complete a total of 30 patients, or to a total of 21 as indicated in the table 9.9. The intent to increase the total AA accrual to 21 needs to be clarified described if in fact the study will remain open to accrue these patients. Will this continue in a randomized fashion? Will an analysis plan be included?
 
The total number of participants in the consent 224 does not match any of these numbers. Please clarify.
 
Response: This is no longer applicable to the study

The following revisions to E3A06 protocol have been made in this addendum:

	Section	Change
1.	Cover Page	Updated Version Date
2.	Contacts Page	Updated [name] contact information
3.	5.2.3	Updated the AE team at ECOG-ACRIN and NCI fax phone numbers
4.	5.3	Updated the Lenalidomide CAEPR list with version 2.8, June 27, 2019.
5.	5.5.2.3	Replaced the 2 remaining mentions of “LCP” with “CPPCP”.
6.	Appendix VI	Deleted “sexually mature” from the definition of FCBP. The italicized paragraph regarding dexamethasone-containing lenalidomide regimens has been deleted.
7.	Appendix VII	Deleted “sexually mature” from the definition of FCBP. Added back the following text in red in the “male” section: Do not donate blood, semen or sperm
8.	Appendix XIII	Clarified what needs to be reported in female patients and CTEP’s phone number

The following revisions to E3A06 Informed Consent Document have been made in this addendum:


The most current version of the study protocol and all supporting documents must be downloaded from the protocol-specific Web page of the CTSU Member Web site located at https://www.ctsu.org. Access to the CTSU members' website is managed through the Cancer Therapy and Evaluation Program - Identity and Access Management (CTEP-IAM) registration system and requires user log on with CTEP-IAM username and password.
		

For clinical questions (i.e. patient eligibility or treatment-related) contact the Study PI of the Coordinating Group
		

For non-clinical questions (i.e. unrelated to patient eligibility, treatment, or clinical data submission) contact the CTSU Help Desk by phone or e-mail: CTSU General Information Line – [name], or [contact]. All calls and correspondence will be triaged to the appropriate CTSU representative.
		

For detailed information on the regulatory and monitoring procedures for CTSU sites please review the CTSU Regulatory and Monitoring Procedures policy located on the CTSU members' website https://www.ctsu.org > education and resources tab > CTSU Operations Information > CTSU Regulatory and Monitoring Policy
		

The CTSU Web site is located at https://www.ctsu.org
		

Schema

- Rev. 7/13
1. Enrollment will be suspended for a phase II safety analysis when the phase II accrual goal is met. Once that has happened, the randomized portion of the trial will begin.
 2. Mobilize stem cells following 4-6 cycles of therapy. While stem cell collection following 4-6 cycles of therapy is suggested strongly, it is not required for protocol participation.
- Rev. 2/12, 7/13
3. Patients are to receive aspirin or an alternative as outlined in Sections 5.1.1 and 5.5.2.1. The suggested dose is 325 mg/day however the dose is at the discretion of the treating physician. Alternative dosing of 75 mg/day or higher is acceptable provided the patient is at low risk of thrombosis.
- Rev.6/14
4. Submission of pre-study specimens per patient consent.

1. Introduction

1.1 Multiple Myeloma (MM)

Multiple myeloma (MM) accounts for 10% of all hematologic malignancies (1-3). For many years, autologous stem cell transplantation (ASCT), alkylator-based chemotherapy, and corticosteroids had been the mainstay of therapy for the disease. Recently, thalidomide, bortezomib, and lenalidomide have emerged as effective single-agents, demonstrating significant clinical activity in relapsed and refractory MM (4-6). The discovery of these drugs has been accompanied by a growing awareness of the importance of bone marrow microenvironmental changes such as induction of angiogenesis, suppression of cell-mediated immunity, and expression of various adhesion molecules and cytokines in disease progression (7,8). The present challenge is to determine how best to incorporate thalidomide, bortezomib and lenalidomide into the therapeutic strategy for myeloma. ECOG has conducted randomized phase III trials incorporating thalidomide and lenalidomide as part of the initial therapy for newly diagnosed symptomatic MM.

1.2 Smoldering Multiple Myeloma (SMM)

Approximately 15-20% of patients with MM are asymptomatic at presentation (9-12). These patients are usually referred to smoldering multiple myeloma (SMM) (2). They are to be distinguished from patients with monoclonal gammopathy of undetermined significance (MGUS) (13, 14). The current definitions of these disorders are described in the Table below.

Criteria for the diagnosis of MGUS, SMM and MM (15-17)

MGUS Serum monoclonal protein < 3 g/dl and bone marrow plasma cells < 10% and absence of anemia, renal failure, hypercalcemia and lytic bone lesions
SMM Serum monoclonal protein \geq 3 g/dl and/or bone marrow plasma cells \geq 10% and absence of anemia, renal failure, hypercalcemia and lytic bone lesions
MM Presence of a serum/urine monoclonal protein, bone marrow plasmacytosis and anemia, renal failure, hypercalcemia, or lytic bone lesions; patients with primary systemic amyloidosis and 30% bone marrow plasma cells are considered to have both multiple myeloma and amyloidosis
Abbreviations: MGUS, monoclonal gammopathy of undetermined significance; SMM, smoldering multiple myeloma; MM, multiple myeloma.

Patients with SMM have a much higher risk of transformation to overt symptomatic myeloma than patients with MGUS. Most patients with SMM progress eventually to symptomatic MM, and the risk of progression is substantially higher than with MGUS (10-20% per year for SMM versus 1% per year from MGUS) (9). The time to progression (TTP) to symptomatic disease is approximately 2-4 years, but differs greatly depending on the definition used for SMM (18). In SMM patients having bone marrow plasma cells (BMPC) \geq 10%, the median time to progression is approximately 2-3 years (19). In a large study by Kyle and colleagues, using the current criteria for SMM the risk of progression was approximately 10% per year, a rate much higher than observed with MGUS (12).

Rev. 7/13, 12/13

1.3 Targeted Patient Population

The above points support the use of lenalidomide as the experimental arm. The current standard of care for SMM is observation alone with no therapy (1), justifying observation as the control arm. Additionally, in the current trial, we propose to evaluate those patients with SMM who have the highest risk of progression to symptomatic MM. Based upon published data by Kyle et al (12) and Dispenzieri et al (23), we propose to limit eligibility to the highest risk smoldering myeloma patients. Kyle's study cohort (12) is classified into three prognostic groups as follows: high-risk $\geq 10\%$ BMPC and serum M-protein ≥ 3 gm/dl, intermediate-risk $\geq 10\%$ BMPC and serum M-protein < 3 gm/dl and low-risk $< 10\%$ BMPC and serum M-protein < 3 gm/dl.

Rev. 12/13

Dispenzieri et al (23) further divided patients based on the free light chain (FLC) ratio. The normal reference range for FLC ratio is 0.26-1.65. In the Dispenzieri study, 90% of patients were abnormal based on this definition. To discern whether the extent to which FLC ratio was abnormal had an impact, they evaluated the prognostic effect of continuous FLC ratio and found an optimal breakpoint of the FLC ratio was < 0.125 or > 8.0 . With this range, 60% of patients were abnormal. Risk of progression was approximately 35% at 2 years and 60% at 5 years. This is slightly higher than the risk of progression using the < 0.26 or > 1.65 of 32.5% and 52.6%, respectively. They then constructed a risk stratification model including three risk factors: $\geq 10\%$ bone marrow plasma cells, serum M-protein ≥ 3 gm/dl and FLC ratio less than 0.125 or greater than 8. For our trial, high- and intermediate-risk patients based on the Kyle stratification are eligible for entry in the study if they also have an abnormal free light chain ratio defined as < 0.26 or > 1.65 . Given the published natural history of these patients, it will be easier to show benefit for these patients, and they have the highest risk of progression to symptomatic myeloma.

Rev. 7/13

1.4 Lenalidomide

Single agent lenalidomide has shown responses in approximately one-third of patients with advanced MM, even if patients had previously failed thalidomide (36). In combination with dexamethasone, lenalidomide was active in approximately 60% of patients with advanced relapsed MM (37, 38), and over 90% of patients with newly diagnosed symptomatic MM (30-32). Thus, the drug is likely to have significant activity in patients with asymptomatic MM who are at an earlier stage the disease. This hypothesis has been previously tested with thalidomide, where the activity observed with thalidomide in relapsed MM did translate into significant activity in the asymptomatic stage (25,39). Lenalidomide is a safer and more potent analog of thalidomide, and there is no reason to believe that the drug will fail to act in the asymptomatic stage. Additionally, for patients who achieve long lasting and deep responses to lenalidomide based therapy, there is a history of chronic administration of lenalidomide for periods far longer than other therapies in the setting of relapsed and newly diagnosed myeloma. The net result of these observations is that lenalidomide is an active agent with a good safety profile in the acute and chronic administration setting, and is an ideal agent to test in a patient population that is at high risk of progression to symptomatic myeloma, yet to date has not proven to benefit from early therapy.

In a phase II trial of 122 patients with relapsed myeloma, approximately 25% responded to single-agent lenalidomide therapy (40). This trial included several patients who had earlier failed thalidomide. Typical dosing for lenalidomide is 25 mg per day on days 1-21 of a 28 day cycle. The most common adverse effects are thrombocytopenia and neutropenia. Side effects such as sedation, constipation, and neuropathy appear to be less common with lenalidomide.

The clinical efficacy of lenalidomide was established in two recent phase III trials, where patients with relapsed refractory MM had superior response rates, TTP and overall survival with lenalidomide plus dexamethasone compared to dexamethasone/placebo (37,38).

In a trial among newly diagnosed MM patients, the combination of lenalidomide plus dexamethasone has shown remarkable activity with responses in more than 90% of patients (30,31).

Additional rationale for the current trial was generated when the closely related analogue thalidomide was shown to improve TTP in another trial of SMM, but its use was limited by the development of peripheral neuropathy (25).

The risk of deep vein thrombosis (DVT) with lenalidomide is one concern; however this risk appears to be limited to patients receiving high dose dexamethasone plus lenalidomide;(41) the risk does not seem to be increased when lenalidomide is used as a single-agent (42) or when the drug is used in combination with lower doses of dexamethasone (41).

Lenalidomide has anti-angiogenic and immunomodulatory properties (43). Therapy targeted against angiogenesis presents an exciting, new and possibly less toxic way to treat malignant disease. There is evidence that increased bone marrow angiogenesis occurs in myeloma and is correlated with the plasma cell labeling index (PCLI; a measure of plasma cell proliferative activity) (44,45). Angiogenesis has also been shown to be a powerful prognostic factor in newly diagnosed MM, and it increases as patients progress from asymptomatic to symptomatic disease (24,46,47).

To better study the risks of lenalidomide in this asymptomatic patient population, we have built in a pilot phase prior to the start of the randomized phase of the trial.

Rev. 7/13

1.5 Rationale and Hypothesis for Current Study

Over the years due to lack of effective therapy, patients with SMM have been observed without therapy. However, with the discovery of new active agents, the time has come to test therapeutic intervention in asymptomatic MM with the goal of delaying progression to symptomatic MM because of the following reasons:

- i) Once symptomatic, MM is incurable, and symptoms from MM such as bone fractures can be debilitating. Patients with asymptomatic MM who will be considered for this study will be at high risk of progression to symptomatic MM. The median time to progression is approximately 18 months in patients who have no bony lesions.(19) The presence of bone lesions on skeletal survey or magnetic resonance imaging greatly increases the risk of progression in asymptomatic MM.(9, 20-22) Patients with abnormal peripheral blood monoclonal plasma cell studies defined as an increase in the number or proliferative rate of circulating plasma cells by immunofluorescent

assays are at higher risk for earlier progression to myeloma. In a study of 57 patients, we found the median time to progression was 9 months for those with abnormal peripheral blood monoclonal plasma cell studies versus 30 months for those with normal studies. ($P < 0.01$) (19). More recently, the serum free light chain (FLC) ratio has been shown to be a significant adverse predictor of outcome, and the test is widely available. Patients with bone marrow plasma cells 10% or more and an abnormal FLC ratio have a median progression free survival (PFS) of 2.3 years, and a 2 year PFS rate of 58.5% (23).

- ii) As discussed later, progression to symptomatic MM likely involves an angiogenic switch, similar to the progression of in-situ carcinomas to an invasive phenotype (8, 24). Thus there is mechanistic rationale for anti-angiogenic agents such as lenalidomide to delay progression.
- iii) There is strong preliminary data from a phase II trial at Mayo Clinic that the related agent thalidomide is effective in asymptomatic MM with evidence suggesting a delay in time to progression based on historical controls (25).
- iv) Single agent lenalidomide is an attractive new option that is ideally suited for testing in asymptomatic MM (6, 26). The drug does not appear to have much of the non-hematologic side-effects that have been a problem with the use of thalidomide in this population such as peripheral neuropathy (6,27,28). It has shown remarkable activity in relapsed and newly diagnosed MM (29,30). Lenalidomide is orally administered making it convenient for long term therapy in an asymptomatic population. Incidentally, there is remarkable interest in this agent as initial therapy as evidenced by the rapid accrual to ECOG E4A03 trial with lenalidomide in newly diagnosed MM.
- v) There is evidence from Mayo and ECOG studies that therapy with lenalidomide does not adversely affect stem cell collection (30-32). Some reports have found problems with stem cell mobilization with growth factors alone (33), which is resolved with the use of growth factor plus cyclophosphamide (34). This appears to be an effect of lenalidomide on adhesion molecules, rather than toxicity to stem cells since patients can successfully mobilize with cyclophosphamide (34, 35).
- vi) Given the toxicity of stem cell transplantation and current MM therapy, and given the destructive bone lesions that characterize MM, there is a strong patient demand for novel therapeutic options that would delay progression to symptomatic MM, rather than observation without therapy.

Patients and physicians alike desire a way to delay progression in patients with SMM. Currently, such patients are observed without therapy even though the risk of progression is high. Symptomatic MM has a median survival of 3–4 years and is associated with significant morbidity from destructive bone lesions, renal failure, and infections. Therapy includes aggressive chemotherapy regimens including stem cell transplantation, but is not curative. With the advent of new, non-cytotoxic agents with novel mechanisms of action that target critical steps in MM pathogenesis, there is a great need for clinical trials using these agents. There is little question whether lenalidomide can induce responses in patients with SMM. The more important end-point is demonstration of a superior PFS with lenalidomide compared to observation, especially considering the costs and possible side-effects of therapy. Therefore, a randomized, phase III trial is

necessary. Overall survival differences between lenalidomide and observation need to be studied; however, overall survival as a primary end-point has become unrealistic given the rapid advances in new therapeutic options available to patients at the time of relapse, and the protracted time it would take to complete in patients with SMM in which the median overall survival is likely to be in excess of seven years.

We are confident that this phase III trial will be successful in improving progression-free survival of SMM (the primary endpoint), and further, will have the potential to effect a paradigm shift in the treatment of early stage MM. If the endpoints of the trial are successfully met, the benefits of therapy far outweigh the risks. There is strong preliminary data supporting a role for use of lenalidomide in this setting, a therapy that overcomes much of the limitations previously seen with agents like thalidomide, melphalan, or corticosteroids. In sum, per detailed discussions with NCI/CTEP and various cooperative groups, this trial is felt to be of major importance and will be done collaboratively by ECOG-ACRIN and SWOG.

Rev. 12/13

1.5.1 Modifications in Addendum #8:

In Addendum #8, we are modifying the inclusion criteria in response to emerging data in the smoldering MM arena. The first modification is to relax the free light entry criteria. We are continuing to exclude patients with a normal free light ratio as they have a very low risk of conversion. However, we are now amending to allow any free light chain abnormality (abnormal ratio) to enroll. This change is being made to allow further exploration of the potential benefit of early treatment among patients with abnormal but not at the extremes free light chain ratio. The second change is to allow for patients diagnosed with smoldering MM to be enrolled if within 5 years of diagnosis of smoldering MM as opposed to 1 year. This modification is to bring our trial into more alignment with what is being reported by the PETHEMA group in their current high risk smoldering clinical trial. Research on the natural history of SMM published by Kyle et al (12) in an unselected SMM cohort show the risk of progression over the first 5 years is 10% per year, approximately 3% per year for the next 5 years and 1% per year for the last 10 years. This suggests that broadening eligibility by years since diagnosis from 1 to 5 likely will not have a significant impact on PFS estimates. Additionally, patients will be stratified at randomization according to time since diagnosis of SMM: (1 year vs. > 1 year).

1.6 Quality of Life Assessment

1.6.1 Background and Significance

The Quality of Life (QOL) of MM patients is determined by disease specific symptoms and treatment specific side-effects. Patients with SMM participating in E3A06 are required to be asymptomatic from disease and must be MM specific treatment naive. Patient reported outcome (PRO) assessment as part of E3A06 is designed to describe symptoms of MM specific disease progression as well as potential side-effects from treatment intervention. The PRO instrument chosen

consists of the Functional Well Being (FWB) and Physical Well Being (PWB) components of the Functional Assessment of Cancer Therapy - General (FACT-G) (48). This instrument has been validated extensively and has been incorporated into our ongoing E1A05 and E1A06 phase III MM treatment trials. For the purpose of a comprehensive, disease specific QOL assessment in symptomatic MM patients we will also utilize the Multiple Myeloma Subscale (MMS). This MM specific novel instrument, as described in detail in 6.3.1, has been developed by interviewing MM patients, describing and quantifying their disease and treatment specific symptoms as well as by incorporating the cumulative experience of MM expert physicians.

1.6.2 Hypothesis

We hypothesize that the combination of the functional well-being (FWB) and physical well-being (PWB) components of the FACT-G (14 questions) will assess the overall functional and physical well-being and serious toxicities experienced by SMM patients and correlate with the impact of a specific treatment intervention in terms of progression free survival. The primary endpoint for this quality of life assessment is best assessed at the end of cycle 24 treatment since at this point patients will have experienced both acute and chronic toxicities, if any, and beyond two years, more and more patients will drop out due to disease progression.

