7. QOL timepoints: At registration (+ 7 days) prior to initiation of treatment or observation; the last day (+ 7) of cycles 6, 12, 18, 24, 30, 36, 42, and 48; and at the end of treatment or observation (+14 days). For patients that discontinue protocol therapy or go off observation early not due to disease progression, QOL will also be assessed at the next quarterly Long Term follow-up visit (+ 14 days). After this, patients will not be followed further for QOL.
8. If leg swelling or pain is present in legs, an ultrasound of the legs will be done for deep vein thrombosis.
9. Bone marrow biopsy or aspirate performed to evaluate plasma cells %, presence of sheets of plasma cells and presence of plasma cell clonality. Absence of plasma cell clonality required for sCR.
10. Needed if urine M-spike at study entry was ≥ 200 mg/24 hr or if VGPR needs to be documented.
11. Patients will be followed for progression every 3 months if patient is < 2 years from study entry, every 6 months if patient is 2-5 years from study entry, every 12 months if patient is 6-10 years from study entry. No specific requirements if patient is more than 10 years from study entry. Patients will be followed for survival only once progression occurs and study treatment ends.
12. To be repeated every year or if clinically indicated for progression or symptoms.
13. To be assessed every 4 months.
14. All patients must be counseled about pregnancy precautions, risks of fetal exposure and other risks. The counseling must be done on Day 1 of each cycle (or at a minimum of every 28 days) and at drug discontinuation. The Lenalidomide Education and Counseling Guidance Document ([Appendix VII](#)) must be completed and signed by a trained counselor at the participating site prior to each dispensing of lenalidomide treatment. A copy of this document must be maintained in the patient records. A Lenalidomide Information Sheet ([Appendix VIII](#)) will be supplied to each patient receiving lenalidomide treatment. The patient must read this document prior to starting lenalidomide study treatment and each time they receive new supply of study drug.
- Rev. 8/11 15. Only enough lenalidomide for 28 days or one cycle of study treatment may be provided to the patient each cycle.
- Rev. 8/11 16. TSH should be tested for Arm A ONLY and then only when clinically indicated by the Principal Investigator.
-

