9.7 Quality of Life

9.7.1 Primary QOL Endpoints

Quality of life assessment is performed in an identical fashion in both arms A and B and will be administered to both arms on the same schedule and frequency. The QOL assessment utilizing the FACT-

FWB+PWB and MMS instruments will first be administered at registration (+ 7 days) prior to initiation of treatment or observation. During the treatment or observation period, QOL will be measured every 6 cycles (day end + 7 days) and at the end of treatment or observation (+ 14 days). For patients that discontinue protocol therapy or go off observation early not due to disease progression, QOL will also be assessed at the next quarterly Long Term follow-up visit (+ 14 days). After this, these patients will not be followed further for QOL. Patients will be asked to complete the QOL questionnaire just prior to meeting with health care providers at scheduled visits. This should reduce the impact of health care related information upon perceived QOL.

The FACT-FWB+PWB PRO instrument has 14 items and the score ranges from 0-56. The primary endpoint for the QOL study will be defined as the mean change of the FACT-FWB+PWB score from registration (prior to randomization) to cycle 24. The null hypothesis is that the FACT-FWB+PWB mean change score between the two groups is the same over this time period. Based on the length of this PRO instrument, a minimal absolute difference in means change scores of the two arms of 4-6 is considered clinically significant between two groups.(70) Nevertheless, for this analysis the difference in drug-related QOL must be much greater to overcome a significant PFS benefit. The FACT- FWB+PWB domains are reported to have a standard deviation (SD) of 11. (Personal Correspondence with [name] dtd 12.26.08)

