Differences in FACT-FWB+PWB mean change scores between the treatment arms from time of registration to cycle 24 that can be detected with 80% power are presented in following table. The expected hazard rates on each arm served to establish patients alive without PD at the end of the interval. Sensitivity for the % of patients alive without PD (n=55 patients given expected hazard rates) assumed to complete the questionnaire at the end of cycle 24 (compliance rates of 55%, 70%, 85%), allowing for slightly more variability in the instrument (11.0, 12.0) and assuming different correlation (0.4, 0.6, 0.8) between repeated measures was performed. For example, assuming a SD of 11.0 for the FACT-FWB+PWB, a correlation between repeated measures of 0.6 and using a two-sided t-test with a 0.05 significance level, there is sufficient power to detect a true difference in the FACT-FWB+PWB mean change score between the two arms of 7.3-9.2. Given our chosen interval for the primary endpoint and the reduced sample size with the redesign, we will only be able to detect large differences in mean change score between arms at expected compliance rate (70%).

Differences detected with 80% power between Treatment Arms in Mean Change Score from Registration to end of Cycle 24: FACT-FWB+PWB					
standard deviation (SD)	correlation	SD of change	55% compliance n=30	70% compliance n=38	85% compliance n=56
11.0	0.4	12.05	11.2	9.9	9.0
	0.6	9.84	9.2	8.1	7.3
	0.8	6.96	6.5	5.7	5.2
12.0	0.4	13.15	12.2	10.8	9.8
	0.6	10.73	10.0	8.8	8.0
	0.8	7.59	7.1	6.2	5.7

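### The primary quality-of-life comparison at cycle 24 should be estimated from a baseline-adjusted repeated-measures model of the forms already collected, and its detectable-difference table restated

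*Combined protocol and SAP*

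**What the plan says.** Section 1.6.2 gives the timing: "The primary endpoint for this quality of life assessment is best assessed at the end of cycle 24 treatment". Section 9.7.1 defines the primary QOL endpoint as the "mean change of the FACT-FWB+PWB score from registration (prior to randomization) to cycle 24". The null hypothesis is that the "mean change score between the two groups is the same over this time period". Sensitivity is worked out "using a two-sided t-test with a 0.05 significance level" and 80% power. The inputs are an SD of 11 or 12, a correlation of 0.4, 0.6 or 0.8, and compliance of 55%, 70% or 85% among 55 patients alive without progression. The text does not say whether 55 is per arm or in total. At SD 11 and correlation 0.6 the table prints 9.2, 8.1 and 7.3 points.

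Section 9.7.1 calls a difference of 4-6 points clinically significant, then adds that a much greater one would be needed to outweigh a PFS benefit. It concedes that only large differences are detectable at 70% compliance, and blames both the chosen interval and the smaller sample after the redesign.

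Footnote 7 of Section 7.1 schedules forms on "the last day (+ 7) of cycles 6, 12, 18, 24, 30, 36, 42, and 48", and 9.7.1 says both arms follow the same schedule. Section 9.7.2 puts the interval forms into a mixed model, with joint modelling of scores and time to dropout. Its stated contrast is patients with progression versus patients without, not R versus Obs.

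**The concern.** A change score subtracts the baseline in full. At correlations of 0.4 to 0.8 this is less precise than using the baseline as a covariate. The contrast also needs a cycle 24 form. Patients who stop early without progression have an end-of-treatment form and one quarterly follow-up form, and then QOL collection ends (Sections 6.3.2 and 9.7.1). Those who stop for toxicity will therefore usually have no cycle 24 form, and their earlier forms are not used to compare the arms.

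The patients are asymptomatic and the control is observation, so the QOL cost of treatment is part of judging any PFS gain. A needlessly imprecise comparison makes a null QOL result harder to interpret. The sponsor's view of what the study can detect also rests on a table that does not match its description.

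**Working it through.** **1. The printed table.** The SD of a change is SD × √(2(1 − ρ)). For SD 11 and ρ = 0.6 this is 11 × √0.8 = 9.84, as printed; all six SDs of change reproduce. The detectable differences do not. Noncentral t, SD of change 9.84, for 55% / 70% / 85% compliance:

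| Calculation | n | Result |
|---|---|---|
| Printed | 30 / 38 / 56 | 9.2 / 8.1 / 7.3 |
| Stated test: two-sided 0.05, 80% power, n per arm | 30 / 38 / 46 | 7.2 / 6.4 / 5.8 |
| Stated test, n in total | 30 / 38 / 46 | 10.4 / 9.2 / 8.3 |
| One-sided 0.05, 80% power, n in total | 30 / 38 / 46 | 9.16 / 8.09 / 7.33 |
| Two-sided 0.025, 90% power, n per arm | 30 / 38 / 46 | 9.15 / 8.09 / 7.33 |

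Each of the last two rows reproduces all 18 printed cells to rounding, but neither is the test described. Both need 46 in the 85% column. Since 0.85 × 55 = 46.75, the printed 56 does not follow from 55.

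**2. Expected cycle 24 forms.** Inputs from Section 9.4: 90 per arm, hazards 0.0279 (Obs) and 0.011 (R) per month. The end of cycle 24 is 24 × 28 = 672 days, or 22.08 months.

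- Obs: 90 × exp(−0.0279 × 22.08) = 90 × 0.540 = 48.6 progression-free; × 0.70 = 34.0 forms.
- R: 90 × exp(−0.011 × 22.08) = 90 × 0.784 = 70.6 progression-free; × 0.70 = 49.4 forms.

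The two arms sum to about 119 progression-free patients, so 55 looks like a per-arm figure rather than a total.

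**3. Same contrast, three estimators.** Normal quantiles: 1.960 + 0.842 = 2.802. √(1/34.0 + 1/49.4) = 0.2228.

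- Change score: 2.802 × 9.84 × 0.2228 = 6.1.
- Baseline-adjusted, cycle 24 only: the SD is 11 × √(1 − 0.6²) = 8.8, so 2.802 × 8.8 × 0.2228 = 5.5.
- Repeated-measures model of registration and cycles 6, 12, 18 and 24: 5.2. This is 2.802 times the standard error from the expected information matrix, with a common baseline mean, arm-by-visit means, loss at progression on the plan's hazards and independent 70% compliance at each visit.

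At SD 11 and 70% compliance:

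| ρ | Change score | Baseline-adjusted | Model, cycle 24 | Model, average of cycles 6-24 |
|---|---|---|---|---|
| 0.4 | 7.5 | 6.3 | 6.1 | 3.5 |
| 0.6 | 6.1 | 5.5 | 5.2 | 3.2 |
| 0.8 | 4.3 | 4.1 | 3.9 | 2.5 |

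At ρ = 0.6, power for a 5-point difference at cycle 24 rises from 63% to 76%. The variance ratio is (6.14/5.23)² = 1.38, so the gain is worth about 38% more patients. If the correlation decays with time, with 0.6 between registration and cycle 24, the model gives 4.8 at cycle 24 and 3.0 for the average.

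**4. If 55 is a total.** Scaling to 55 progression-free patients in all, at ρ = 0.6, the cycle 24 contrast goes from 9.0 (change score) to 7.7 (model), and the average is 4.8.

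**The case against.** Cycle 24 was chosen for a reason: Section 1.6.2 wants both acute and chronic toxicity to have been experienced. That stands. A reader might infer from the 3.2 that the endpoint should become the average over cycles 6-24, but the average answers a different question. If the effect grew linearly to cycle 24, the mean weight is (0.25 + 0.5 + 0.75 + 1)/4 = 0.625, and 3.2/0.625 = 5.1, about what the model gives at cycle 24. If it appeared equally at cycles 18 and 24 only, 3.2/0.5 = 6.4, slightly worse than the planned 6.1. If it appeared at cycle 24 only, 3.2/0.25 = 12.8. The null's reference to a time period does not require an average either, since it can be read as the change from the start to the end of that period.

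A reader might also infer that the unused forms are why only large differences are detectable, or that the plan misses its own 4-6 point target. The documents support neither. Beyond baseline adjustment the interim forms add about 0.3 point (5.5 to 5.2). Section 9.7.1 also names the reduced sample size, and the printed 8.1 is already 6.4 under the stated test with 38 per arm. The 4-6 points are a benchmark of clinical significance, and the plan asks for much more to offset a PFS benefit. Nor are the forms wholly unused, because 9.7.2 analyses them for another contrast.

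The model assumes data missing at random, while 9.7.2 expects heavy and possibly informative missingness. That limitation is real. It calls for a sensitivity analysis; the two-form test does not avoid it, since it rests on completers alone.

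**Conclusion.** The point holds as a low-cost gain in precision for the existing endpoint, together with a table that must be corrected. It is not a case for replacing the endpoint. At cycle 24 the detectable difference falls from about 6.1 to 5.2 points at ρ = 0.6, from 7.5 to 6.1 at 0.4, and from 4.3 to 3.9 at 0.8. Baseline adjustment supplies most of this. These figures rest on the plan's hazards, 90 per arm, SD 11, exchangeable correlation, data missing at random, and 70% compliance at every visit, which the plan states only for cycle 24. Stopping without progression is not modelled, so actual form counts could be lower.

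The table finding needs none of those assumptions. The printed differences do not follow from a two-sided 0.05 test with 80% power, whether n is per arm or in total.

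**What to change.** In Section 9.7.1:

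1. Keep cycle 24 as the primary time point. Estimate R minus Obs there from one repeated-measures model of the registration and cycle 6, 12, 18 and 24 forms, with a common baseline mean, arm-by-visit means and unstructured covariance. State how end-of-treatment forms that fall between scheduled visits are handled.
2. Report the average over cycles 6-24 from the same model as a supportive contrast only, because it gives less weight to chronic toxicity.
3. Apply the joint model of scores and time to dropout already cited in 9.7.2 to this comparison of the arms, as a sensitivity analysis.
4. Restate the table: give sidedness, alpha and power, say whether n is per arm or in total, and reconcile n=56 with 85% of 55 (46 to 47).

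The cost is analysis-plan text and programming. Because the primary time point does not change, patients already enrolled are unaffected. The amendment should be dated and made before QOL data are compared by arm.
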